## 5.2. Secondary Analyses

Summary statistics of all domains of the NPI will be computed for the observed and change from baseline values in the Evaluable and ITT populations. Summaries of other secondary endpoints will be computed for the observed and change from baseline values in the Evaluable population.

Supporting analyses of the secondary endpoints may be performed stratifying by randomization strata if there are sufficient numbers of patients within each strata.

## **Quantitative Endpoints**

The quantitative secondary efficacy endpoints will be assessed by analyzing the change from baseline to the 10-week time point in the Evaluable population using PROC MIXED to model the difference in the Week 10 change from baseline score between treatment groups and to handle missing assessments. The change from baseline to each scheduled post-baseline visit will be estimated using repeated measures mixed models assuming data are missing at random, with covariates for baseline and visit. The lower 95% confidence limit of the difference in mean scores at Week 10 (MP-101 minus Placebo) will be estimated from the mixed model. The effects of baseline domain scores and treatment will be allowed to vary across visits. The following SAS code will be used, for assessments at Weeks 2, 4, 6, and 10. For patients who withdraw prior to Week 10, NPI data from the early termination visit will be used as the next visit's assessment; for example, if a patient's last scheduled assessment is at Week 4, the early termination data will be included in the analysis as Week 6.

proc mixed;

class visit treatment patient; model psychosis=visit\*baseline visit\*treatment / s; repeated visit / type=vc subject=patient; random patient; estimate 'Trt Effect, week 10' visit\*treatment 0 0 0 0 0 0 1 -1/cl alpha=.10; run; In addition, plots of each least squares mean domain score ( $\pm$  standard error) for the psychosis, delusions, hallucinations, agitation/aggression, and total scores by scheduled visit will be created.

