#### 2.10. Adjustment for Covariates

Where possible, analyses will adjust for the baseline value of the endpoint and by the four baseline randomization strata, i.e.:

- MMSE < 16, eGFR < 60
- MMSE < 16, eGFR  $\ge$  60
- MMSE  $\geq$  16, eGFR < 60
- MMSE  $\geq$  16, eGFR  $\geq$  60

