#### Mini-Mental State Examination (Folstein et al., 1975)

The MMSE is a simple, 30-question, pen-and-paper test that evaluates attention, orientation, memory, registration, recall, calculation, language, and the ability to draw a complex polygon. The range for the total MMSE score (i.e. the total number of correctly answered items) is 0 to 30, with lower scores indicating greater impairment. If any individual item is missing, the MMSE score will be set to missing.

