## 5.3. Exploratory Analyses

The exploratory efficacy objectives to determine whether MP-101 is superior to placebo in patient behavior and caregiver burden will be assessed using the same methods as the secondary endpoints.

The effect of HTR2A and ApoE genotypes on response to treatment, and the exposure-response relationships between efficacy and safety endpoints, may also be explored, as needed. If performed, these analyses will be described in the CSR.

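### SAP 5.2 names the lower confidence limit for all quantitative endpoints, which does not bear on superiority for 15 of 16 of them, and its model omits the strata that SAP 2.10 calls for

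*SAP*

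**What the plan says.** **The limit.** SAP 5.2 (Quantitative Endpoints) names one inferential quantity: "The lower 95% confidence limit of the difference in mean scores at Week 10 (MP-101 minus Placebo) will be estimated from the mixed model". The SAS code ends its estimate statement with "0 0 0 0 0 0 1 -1/cl alpha=.10", which requests a two-sided 90% interval. SAP 5.3 says that the exploratory efficacy objectives "will be assessed using the same methods as the secondary endpoints". Those objectives include MMSE, whose range "is 0 to 30, with lower scores indicating greater impairment". The SAP also names the lower limit for the two response rates (5.1 and 5.2, Ordinal Endpoints), where a higher rate is better.

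**The strata.** SAP 2.10 says: "Where possible, analyses will adjust for the baseline value of the endpoint and by the four baseline randomization strata". The model in SAP 5.2 is described as "repeated measures mixed models assuming data are missing at random, with covariates for baseline and visit", and its class statement reads "class visit treatment patient", with no stratum variable there or in the model statement. Earlier in SAP 5.2 there is an optional provision: "Supporting analyses of the secondary endpoints may be performed stratifying by randomization strata if there are sufficient numbers of patients within each strata". Protocol 10.3.3.2 puts the stratification factors, with baseline, in this same mixed model.

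**The concern.** The stated objective for these endpoints is superiority to placebo. An NPI domain score is severity times frequency, and ZBI-22 adds up ratings of burden, so a fall is an improvement and a beneficial MP-101 minus placebo difference is negative. The lower limit then says how large the benefit could be. Whether there is a benefit depends on the upper limit, which the text does not call for. SAP 5.2 gives no decision rule from which a reader could work out the intended use.

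The wording matches that for the response rates, where it is correct. Here it is applied to scores that run the other way, including psychosis, the score modelled in the SAP's own example code.

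On the strata, a programmer cannot follow both SAP 2.10 and SAP 5.2. If the choice of limit or of model is left until after unblinding, it can be challenged as made with the results in view.

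**Working it through.** **1. Level of the limit.** A two-sided interval at alpha 0.10 uses z = 1.645, as does a one-sided 95% limit. The code therefore prints both one-sided 95% limits, and the stated level is right. The fault lies in which limit the text says to report.

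**2. Count of endpoints.** The SAP gives no single list, so this count is assembled from SAP Table 1 and Protocol 10.3.3.2.

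- Secondary, quantitative: NPI Total, Core Total, Caregiver Distress, anxiety = 4 (CGI-I is handled as ordinal)
- Continuous scores added by Protocol 10.3.3.2: psychosis, agitation/aggression = 2
- Exploratory NPI domains = 8
- ZBI-22 = 1
- MMSE = 1

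The total is 4 + 2 + 8 + 1 + 1 = 16, of which 15 are better when lower. Adding delusions and hallucinations, whose least squares means are plotted, gives 17 of 18. Adding UPDRS Part III as well gives 18 of 19. MMSE is the only exception in each count.

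**3. What each limit can show.** Use normal theory with the difference in units of its standard error (SE). Take a benefit that the upper limit detects with 80% power: −(1.645 + 0.841) = −2.486 SE.

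| | No effect | Benefit of 2.486 SE |
|---|---|---|
| P(lower limit < 0) | Φ(1.645) = 0.95 | Φ(1.645 + 2.486) = Φ(4.131) = 0.99998 |
| P(upper limit < 0) | Φ(−1.645) = 0.05 | Φ(2.486 − 1.645) = 0.80 |

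The lower limit barely separates the two cases.

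As an illustration, take 40 per arm with a benefit of 0.3 SD (assumed; the documents give no SDs or effects for these scores). The SE is √(2/40) = 0.2236 SD, and the expected limits are −0.3 ± 1.645 × 0.2236 = −0.668 and +0.068. The lower limit is well below 0, yet superiority is not shown.

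**4. Sign convention.** The SAP does not define the direction of change for efficacy scores. There are two cases:

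- Follow-up minus baseline: the named limit is on the wrong side for 15 of 16.
- Baseline minus follow-up: it is on the wrong side for 1 of 16 (MMSE).

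The first is the usual meaning and fits the SAP's reference to a difference in mean scores. With baseline in the model at each visit, the treatment difference is the same whether the response is the score itself or follow-up minus baseline. Neither convention makes one named limit right for every endpoint.

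**5. Cost of omitting strata.** Let R² be the share of residual variance explained by the strata. The documents give no figure, so a range is assumed. Width ratio = 1/√(1 − R²); one-sided error = P(Z > 1.645/√(1 − R²)).

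| R² | Width ratio | One-sided error |
|---|---|---|
| 0 | 1.000 | 5.0% |
| 0.02 | 1.010 | 4.8% |
| 0.05 | 1.026 | 4.6% |
| 0.10 | 1.054 | 4.1% |

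A simulation of 20,000 trials (80 patients, four strata, stratified allocation, analysis of covariance at a single visit) gave width ratios of 0.999, 1.010, 1.026 and 1.055. One-sided error was 5.2%, 4.9%, 4.5% and 4.3% without strata, and 5.3%, 5.1%, 4.9% and 5.1% with them. It simplifies the four-visit model.

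If the strata explain nothing, adding them costs 3 degrees of freedom. The t quantile at 74 rather than 77 degrees of freedom is larger by a factor of 1.0005, about 0.05%.

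**6. Feasibility.** A repeated-measures mixed model with a four-level stratum factor was fitted without difficulty to simulated data on 80 patients.

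**The case against.** **On the limit.** The count of 15 of 16 depends on a sign convention that the SAP leaves open, and the SAP defines response in terms of improvement. If change were coded as improvement, the count would fall to 1 of 16. The code prints both limits, so no estimate or information is lost. These endpoints are secondary or exploratory, with no multiplicity control. The probabilities for the lower limit also do not describe a decision rule in the SAP, because it has none.

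Much of this is fair. The fault is in the reporting text and not in the estimation, and the probabilities measure how informative the named limit is, not the error rates of the plan. But the SAP nowhere defines a reversed sign, and a reversal would still leave MMSE with the wrong limit.

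**On the strata.** SAP 2.10 is a general default hedged by feasibility. SAP 5.2 is the specific section, its text and code agree with each other, and its condition on patient numbers suggests a worry about sparse strata. The SAP also takes precedence over the protocol (SAP 1.1).

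The precedence clause does settle the difference from Protocol 10.3.3.2, but it cannot settle a conflict between two SAP sections. The condition on numbers is attached to optional supporting analyses. It gives no reason for leaving a three-degree-of-freedom factor out of the main model, and such a factor is feasible here. It stands that the numerical effect is small and rests on assumed R² values.

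**Conclusion.** Both parts hold and should be fixed.

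With change as follow-up minus baseline, the limit named in SAP 5.2 does not bear on superiority for 15 of 16 quantitative efficacy endpoints. It is right only for MMSE, and no single sign convention makes it right for all.

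The main mixed model leaves out strata that SAP 2.10 says will be adjusted for where possible. The omission causes no bias. For assumed R² from 0 to 10%, it widens the interval by 0% to 5.4% and makes the one-sided error 5.0% to 4.1%, which is conservative.

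The primary Fisher test, the response-rate limits and the sample size are not affected.

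**What to change.** - In SAP 5.2, state that change is follow-up minus baseline.
- For NPI scores, caregiver distress and ZBI-22, report the upper one-sided 95% limit or the full 90% interval. Keep the lower limit for MMSE and the response rates.
- Add the four-level MMSE-by-eGFR strata factor to the class and model statements and to the model text, or say in SAP 2.10 why these models are exempt.

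The cost is a sentence or two of SAP wording and one factor in two lines of SAS. The strata are already held in the randomisation system, and the factor uses 3 degrees of freedom with about 80 patients. Both changes should be made before unblinding.

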## **1.4.** Sample Size Determination

Approximately 100 patients will be enrolled to enable approximately 80 evaluable patients to complete the study through at least Visit 5 (Week 4).

The primary analysis will use a one-sided Fisher's exact test with a 5% type 1 error rate.

If the NPI response rate in MP-101 treated patients is 30% greater than in placebo treated patients (65% vs 35%), with 40 evaluable patients per treatment group there is at least an 80% chance (i.e. Power) that MP-101 will demonstrate superiority to placebo.

The sample size was calculated assuming an expected 20% drop-out rate of patients in each arm prior to Week 4, so that 100 patients are planned to be enrolled to arrive at 40 patients/arm (N=80) in the Evaluable population.

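### The mixed-model code in SAP 5.2 imposes compound symmetry with no fallback or robust standard error, so the Week 10 limits for secondary and exploratory scores can be off in either direction

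*SAP*

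**What the plan says.** The Quantitative Endpoints part of SAP 5.2 describes "repeated measures mixed models assuming data are missing at random, with covariates for baseline and visit" and then gives the PROC MIXED code to be run, "for assessments at Weeks 2, 4, 6, and 10".

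- **Mean model:** "The effects of baseline domain scores and treatment will be allowed to vary across visits".
- **Target:** "The lower 95% confidence limit of the difference in mean scores at Week 10 (MP-101 minus Placebo) will be estimated from the mixed model". The ESTIMATE statement uses `alpha=.10`, which puts 5% in each tail and so agrees with a one-sided 95% limit.
- **Covariance:** "repeated visit / type=vc subject=patient; random patient".
- **Reach:** SAP 5.3 says that the exploratory efficacy objectives "will be assessed using the same methods as the secondary endpoints".

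The SAP names no alternative covariance structure, no order of fallbacks, no sandwich (EMPIRICAL) standard error and no Kenward-Roger adjustment. Protocol 10.3.3.2 also plans repeated measures mixed models but names no structure. SAP 1.1 gives the SAP precedence over the protocol's statistical sections. SAP 2.1 provides for checking the distributions of analysis variables before parametric methods are used, with transformations or nonparametric methods as alternatives. It does not mention covariance.

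**The concern.** A REPEATED statement with `type=vc` and no grouping gives one residual variance and no residual correlation. The random patient effect then adds the same amount to every variance and covariance within a patient. The result is compound symmetry.

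The model reports one contrast, at Week 10, but estimates its standard error from a variance pooled over all four visits. If the spread of scores given baseline is not constant over visits, that pooled value is not the Week 10 variance. The model is also relied on to handle missing assessments. How it uses a patient's earlier visits when Week 10 is missing depends on the assumed correlations.

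At stake are the Week 10 limits for NPI Total, Core Total as a score, the psychosis and agitation/aggression scores, caregiver distress and anxiety, together with the exploratory NPI domains, MMSE and ZBI-22.

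**Working it through.** **1. The plan's own figure.** The SAP states no SD, standard error or power for the quantitative endpoints. Its one figure is for the primary endpoint (SAP 1.4): at least 80% power with 40 evaluable patients per arm, 65% against 35%, using a one-sided Fisher's "exact test with a 5% type 1 error rate". Exact enumeration gives 79.5% at 40 per arm and 81.1% at 41. The continuity-corrected formula gives 40 per arm, and 80/(1 − 0.2) = 100 enrolled. The figure is reproduced to within a point. It supplies the sample size but does not test this point.

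**2. The implied covariance.** V = σ²p·J + σ²e·I, where J is all ones and I is the identity. With σ²p = 0.6 and σ²e = 0.4, for example, every variance is 1.0 and every correlation is 0.6. This uses 2 parameters. An unstructured 4×4 matrix has 4×5/2 = 10.

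**3. Complete data.** Baseline and treatment effects are free at each visit, so the Week 10 estimate is the same under either structure. Only its standard error changes:

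model SE / true SE = r = √(mean of the four visit variances / Week 10 variance)

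one-sided error = 1 − Φ(1.645·r)

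The SDs are assumptions. In the table they change in equal steps from visit to visit. For a Week 10 SD of 1.3 times the Week 2 SD:

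- mean variance = (1 + 1.21 + 1.44 + 1.69)/4 = 1.335
- r = √(1.335/1.69) = 0.889
- error = 1 − Φ(1.462) = 7.2%

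| Week 10 SD ÷ Week 2 SD | r | One-sided error | 90% interval coverage |
|---|---|---|---|
| 1.5 | 0.843 | 8.3% | 83.4% |
| 1.3 | 0.889 | 7.2% | 85.6% |
| 1.1 | 0.955 | 5.8% | 88.4% |
| 1.0 | 1.000 | 5.0% | 90.0% |
| 0.9 | 1.056 | 4.1% | 91.8% |
| 0.77 | 1.155 | 2.9% | 94.3% |
| 0.67 | 1.264 | 1.9% | 96.2% |

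Uneven steps give similar sizes. SDs of 4, 4.5, 5 and 6 give a mean variance of 97.25/4 = 24.31, r = √(24.31/36) = 0.822 and an error of 8.8%. An unstructured matrix uses the Week 10 variance itself, so r is 1.00 in expectation in every row.

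**4. Simulation of the SAP model.** REML fit, 40 per arm, no treatment effect, 2,000 runs per row. Decaying correlation means 0.8 per two weeks. Dropout is about 20% after Week 4, depends on the Week 4 value, and is an assumption: the documents give 20% before Week 4 and nothing for later.

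| True covariance | Dropout | SE ratio | One-sided error | Coverage |
|---|---|---|---|---|
| Compound symmetry | none | 1.01 | 4.3% | 90.4% |
| Decaying, equal SDs | none | 0.99 | 5.2% | 89.6% |
| Common correlation 0.6, SD rising 1.3 times | none | 0.87 | 7.7% | 84.7% |
| Decaying, equal SDs | about 20% | 0.95 | 4.8% | 88.4% |
| Decaying, SD rising 1.3 times | about 20% | 0.85 | 8.3% | 83.9% |
| Decaying, SD rising 1.5 times | about 20% | 0.81 | 8.9% | 82.3% |
| Decaying, SD falling from 1.3 to 1 | about 20% | 1.08 | 3.3% | 92.8% |
| Decaying, SD falling from 1.5 to 1 | about 20% | 1.17 | 2.7% | 94.8% |

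Monte Carlo error is about 0.5 points on a 5% rate and about 1.6% on an SE ratio. Unequal correlations do no harm with complete data and cost about 5% of the standard error once data are missing. The simulation did not model the SAP's rule that places early-termination NPI data in the next visit's slot. It also did not test for bias in the point estimate.

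**5. MMSE and ZBI-22.** The schedules in the protocol and SAP place their post-baseline assessments at Weeks 4 and 10 only, apart from an early-termination MMSE. With two visits there is only one correlation, so only the equal-variance restriction matters. If the Week 10 SD is 1.3 times the Week 4 SD, r = √((1 + 1.69)/(2 × 1.69)) = 0.892 and the error is 1 − Φ(1.467) = 7.1%.

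**The case against.** The strongest reply is that nothing in the documents shows compound symmetry to be false for any endpoint. With equal variances and complete data, the code gives the right standard error.

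Nor is the direction known. One might expect spread given baseline to widen with time. But NPI domains have a floor, because a negative screening answer ends the questioning, and patients who need rescue therapy are withdrawn. Spread could therefore narrow, in which case the limits are conservative.

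The analyses concerned are supportive. SAP 5.1 rests the primary conclusion on Fisher's test, SAP 2.8 plans no multiplicity adjustment, and no type 1 error rate is set for these endpoints. SAP 2.1 also allows model assumptions to be examined and alternative methods to be reported.

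Most of this stands, and it limits the point to a conditional one on secondary and exploratory results. The appeal to SAP 2.1 is only a partial answer. That section concerns the distributions of variables, and choosing a covariance structure after seeing the data is what pre-specification is meant to avoid.

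A reader might infer that the Week 10 standard error is wrong for every quantitative endpoint, or that the limits are always too narrow. The documents support neither, since they contain no visit SDs or correlations. A reader might also infer that Kenward-Roger would cure the problem. It is a small-sample adjustment under the assumed structure and does not correct a wrong one.

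**Conclusion.** The reading of the code is certain: it is compound symmetry, with no fallback and no robust standard error. The consequence is conditional. Where variances differ by visit, or correlations differ and data are missing, the Week 10 standard error and one-sided 95% limit can be off in either direction.

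For assumed Week 10 SDs of 0.67 to 1.5 times the Week 2 SD, the one-sided error lies between about 2% and 9% instead of 5%. That range rests on assumed SDs, correlations and late dropout. Confidence in the direction and size for any given endpoint is therefore low.

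The scope is the secondary and exploratory quantitative endpoints. For MMSE and ZBI-22 only the equal-variance restriction applies. The primary Fisher test, the Core Total response rate and the CGI-I are unaffected, so the trial's main conclusion is not in question. This is a cheap improvement that should be made, not a condition for the trial to proceed.

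**What to change.** In SAP 5.2:

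- Delete `random patient;`.
- Replace the REPEATED statement with `repeated visit / type=un subject=patient;` and add `ddfm=kr` to the MODEL statement. The unstructured matrix removes the restriction, and Kenward-Roger supplies the small-sample adjustment.
- State in advance the order to follow if the model does not converge: heterogeneous Toeplitz first, then `type=cs` on the REPEATED statement with the EMPIRICAL option and without `ddfm=kr`.

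The cost is two lines of code and a sentence on the fallback. The model then estimates 10 covariance parameters instead of 2 from about 80 patients, or 2×3/2 = 3 instead of 2 for MMSE and ZBI-22. The small convergence risk is covered by the fallback order.

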#### **Ordinal Endpoints**

The Core Total Score response rate will be analyzed using a one-sided Fisher's Exact test. The lower 95% confidence limit of the difference in Core Total Score response rates (MP-101 minus Placebo) will be will be calculated using an exact unconditional confidence interval. The CGI-I will be analyzed using Cochran-Mantel-Haenszel tests using modified Ridit scores (i.e. van Elteren tests).

## 5.3. Exploratory Analyses

The exploratory efficacy objectives to determine whether MP-101 is superior to placebo in patient behavior and caregiver burden will be assessed using the same methods as the secondary endpoints.

The effect of HTR2A and ApoE genotypes on response to treatment, and the exposure-response relationships between efficacy and safety endpoints, may also be explored, as needed. If performed, these analyses will be described in the CSR.

## 6. SAFETY ANALYSES

All analyses of safety including the extent of exposure to study medication will be performed using the Safety population.

## 6.1. Study Medication Exposure and Treatment Compliance

#### **Extent of Exposure**

Patient exposure to study drug will be summarized by the duration of dose administration, the cumulative total dose while in the trial, and the maximum dose taken.

Study drug is administered on site at each visit the dose level is changed, except Visit 2. The last dose will be assumed to have been administered on the day before each drug accountability visit. Therefore, duration of dosing will be calculated as the numbers of days (inclusive) between the first day study drug was taken and the last day study drug was taken. Missing start or end dates will not be imputed.

MP-101 will be provided in a wallet design (blister pack) containing blister strips. Blister packs will be dispensed at Visits 2, 4, 5, and 6 (Weeks 0, 2, 4, and 6, respectively). Each wallet will contain 9 rows of 3 capsules each. For the 20mg active dose, each row contains 1 capsule of active drug and 2 placebo capsules. For the 40mg active dose, each row contains 2 capsules of active drug and 1 placebo capsule. For the 60mg active dose, each row contains 3 capsules of active drug. For patients in the placebo arm, all capsules contain placebo.

The number of capsules taken will be assumed to be 27 times the number of kits dispensed minus the number of capsules returned. For patients while on the 20mg and 40mg dose levels, it will not be possible to know how many active drug capsules were consumed if only partial doses were taken. Therefore, the cumulative total dose taken will be approximated as:

- 20\*(1/3)\*(number of capsules taken while at the 20mg dose level) +
- 40\*(2/3)\*(number of capsules taken while at the 40mg dose level) +

60\*(number of capsules taken while at the 60mg dose level)

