7.1. Treatment Administration

This study compares 60-mg MP-101 versus matching placebo administered orally QD for 10 weeks. Table 7.1 shows the treatment regimens.

Three capsules of 20-mg MP-101 and/or placebo will be ingested with 240 mL of room temperature water with the patient in an upright position. Doses should be administered at approximately the same time in the morning each day. For all visits that include PK sampling, the approximate start and stop times of food consumption prior to dosing and up to 4 hours postdose will be recorded as detailed in Section 9.5.1.

Table 7.1. Treatment Regimens

		Dose	
Treatment Arm	Week 0	Week 1	Week 2 through Week 9
MP-101	20-mg MP-101 QD	40-mg MP-101 QD	60-mg MP-101 QDa
	$(1 \times 20$ -mg caps and	$(2 \times 20$ -mg caps and	$(3 \times 20$ -mg caps)
	2 placebo caps)	1 placebo cap)	
Placebo	Placebo QD	Placebo QD	Placebo QD
	(3 placebo caps)	(3 placebo caps)	(3 placebo caps)

Abbreviations: caps = capsule; QD = once daily; TEAE= treatment-emergent adverse event.

The investigator or designee is responsible for:

- explanation of the correct use of the investigational product(s) to the patient/caregiver/site personnel,
- verification that instructions are followed properly,
- maintenance of accurate records of investigational product receipt, dispensing and collection, and
- return of all unused and used medication to Mediti Pharma, Inc. or its designee at the end of the study.

Note: In some cases, sites may destroy the material if, during the investigative site selection, the evaluator has verified and documented that the site has appropriate facilities and written procedures to dispose of clinical trial materials.

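### The SAP's cumulative-dose formula gives 80 mg for a full day at the 40-mg level and 180 mg at the 60-mg level, overstating exposure about 2.9-fold for a compliant completer who stays at 60 mg

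*SAP*

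**What the plan says.** SAP section 6.1 plans three exposure summaries for the Safety population: duration of dosing, cumulative total dose and maximum dose. Under Extent of Exposure it describes blister rows of three capsules. One is active at the 20-mg level and two are active at the 40-mg level, the rest being placebo. The top level has no placebo: "For the 60mg active dose, each row contains 3 capsules of active drug".

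It then fixes the unit of counting: "The number of capsules taken will be assumed to be 27 times the number of kits dispensed minus the number of capsules returned". It notes that partly taken rows at the 20- and 40-mg levels leave the number of active capsules unknown, and continues: "Therefore, the cumulative total dose taken will be approximated as" the sum of three terms. The first is 20*(1/3) times the capsules taken at the 20-mg level. The second is 40*(2/3) times the "number of capsules taken while at the 40mg dose level". The third is 60 times the "number of capsules taken while at the 60mg dose level".

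Protocol section 7.1 gives the capsule strength and the number taken each day: "Three capsules of 20-mg MP-101 and/or placebo will be ingested with 240 mL of room temperature water". Table 7.1 there shows 1, 2 or 3 active capsules per day at the three levels.

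**The concern.** The quantity being counted is capsules, so each weight should be the average milligrams of active drug in one capsule. That is the capsule strength, 20 mg, times the fraction of capsules in the row that are active (1/3, 2/3 or 3/3). The SAP instead multiplies the whole daily dose (20, 40 or 60 mg) by that fraction. The two agree only at the 20-mg level, where the daily dose happens to equal one capsule.

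Safety and tolerability is a secondary objective, and cumulative dose tells the reader how much drug the safety data rest on. The inflation also depends on how long a patient spent at each level, so dividing the reported totals by a constant would not repair them. SAP section 2.1 relies on independent programming and a check against the plan. Two programmers who both follow the plan would agree on the same wrong number.

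**Working it through.** **Inputs**

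- Active capsule strength: 20 mg (Protocol 7.1).
- Capsules per day and per row: 3 (Protocol 7.1; SAP 6.1).
- Active capsules per row: 1, 2, 3 at the 20-, 40- and 60-mg levels (SAP 6.1; Protocol Table 7.1).
- Unit counted: single capsules, 27 per kit = 9 rows × 3 (SAP 6.1).
- Schedule: step to 40 mg at Week 1 and to 60 mg at Week 2, with 10 weeks of dosing (SAP 2.4; Protocol 7.1). This gives 7 + 7 + 56 = 70 days for a completer not moved down.

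The documents state no cumulative-dose figure to reproduce. The natural test is whether the formula returns 20, 40 and 60 mg for one complete day at each level.

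**Step 1: weight per capsule and result per complete day**

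| Level | SAP weight (mg per capsule) | Content-based weight (mg per capsule) | SAP, 3 capsules | True, 3 capsules |
|---|---|---|---|---|
| 20 mg | 20 × 1/3 = 6.67 | 20 × 1/3 = 6.67 | 20 mg | 20 mg |
| 40 mg | 40 × 2/3 = 26.67 | 20 × 2/3 = 13.33 | 80 mg | 40 mg |
| 60 mg | 60 | 20 × 3/3 = 20 | 180 mg | 60 mg |

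The formula fails the test at two of the three levels.

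**Step 2: totals over the study, full compliance**

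Let C20, C40 and C60 be the capsules taken at each level.

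- SAP: 20 × (1/3) × C20 + 40 × (2/3) × C40 + 60 × C60
- Content-based: (20/3) × C20 + (40/3) × C40 + 20 × C60

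Completer staying at 60 mg: C20 = 7 × 3 = 21, C40 = 7 × 3 = 21, C60 = 56 × 3 = 168.

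- SAP: 140 + 560 + 10080 = 10780 mg
- Content-based: 140 + 280 + 3360 = 3780 mg
- Ratio: 10780 / 3780 = 2.85

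Completer moved down to 40 mg at Week 4: 7 days at 20 mg, 7 + 42 = 49 at 40 mg, 14 at 60 mg, so C20 = 21, C40 = 147, C60 = 42.

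- SAP: 140 + 3920 + 2520 = 6580 mg
- Content-based: 140 + 1960 + 840 = 2940 mg
- Ratio: 6580 / 2940 = 2.24

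| Path | SAP (mg) | True (mg) | Ratio |
|---|---|---|---|
| Stops at end of Week 1 | 140 | 140 | 1.00 |
| Stops at Week 2 | 700 | 420 | 1.67 |
| Stops at Week 4, on 60 mg | 3220 | 1260 | 2.56 |
| Moved down at Week 4, completes | 6580 | 2940 | 2.24 |
| Completes at 60 mg | 10780 | 3780 | 2.85 |

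The completer at 60 mg would appear to have 10780 / 6580 = 1.64 times the exposure of the completer moved down at Week 4. The true ratio is 3780 / 2940 = 1.29.

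**Step 3: could another reading save the formula?**

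- *Capsules meaning rows or daily doses.* The 60-mg weight is then right, but the other two give 6.67 and 26.67 mg per day, which are too low. The completer total becomes 7 × 6.67 + 7 × 26.67 + 56 × 60 = 3593 mg, still not 3780 mg. The count of 27 per kit also rules this reading out.
- *A factor of 1/3 lost from the last line.* The 60-mg term would be correct, but the 40-mg term would still be doubled.
- *The word approximated.* It refers to partly taken rows at 20 and 40 mg. At 60 mg every capsule is active, so nothing needs approximating, and that is where the error is largest.

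**The case against.** The best counter-argument concerns importance, not arithmetic. Cumulative dose is one of three descriptive exposure summaries. Duration of dosing and maximum dose do not use this formula, and missed doses are summarized alongside. No inference depends on it: the primary analysis is Fisher's exact test on NPI response, the secondary models use visit, baseline and treatment, and adverse events are not tested. The QTcF plots use plasma concentration, and the eGFR plot normalizes by the dose at the time of assessment. Exposure-response work is optional and names no metric. No comparison of patients moved down to 40 mg with those kept at 60 mg is planned; patients are grouped by arm. A careful reader might also notice that 60 mg times 70 days is only 4200 mg, well below 10780 mg.

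All of that stands, and it limits the consequence to one descriptive summary. The 2.85 figure also sits near the top of the range: it applies to a compliant completer who stays at 60 mg, and patients who stop early or are moved down have smaller ratios. None of this makes the formula correct. That a reader could detect the inconsistency is no reason to leave it in the SAP.

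**Conclusion.** The concern holds. The 40-mg weight is 2 times too high and the 60-mg weight 3 times too high, judged by the row contents in the same SAP section and the capsule strength in the protocol. The overstatement is 2.85-fold for a completer at 60 mg and 2.24-fold for one moved down at Week 4. It ranges from none to 2.56-fold for the early-stopping paths shown. These totals assume full compliance and visits on the target days; the per-capsule errors need neither assumption. The effect is confined to the descriptive cumulative-dose summary and does not touch the efficacy conclusion. Because following the plan exactly would put a wrong number in a planned safety table, it should be corrected before that table is produced.

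**What to change.** Replace the three-term formula in SAP section 6.1 with:

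Cumulative dose (mg) = 20 × [(1/3) × C20 + (2/3) × C40 + C60],

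where C20, C40 and C60 are the capsules taken at the 20-, 40- and 60-mg levels. This returns 20, 40 and 60 mg for a complete day at each level and 3780 mg for a compliant completer who stays at 60 mg. Those four values can serve as a programming check. The cost is one line of SAP text and the matching line of code. No data collection, dosing rule or other analysis changes.
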